### **Inclusion criteria**

The study will include adult patients with ASA physical status 1–3, requiring surgery for an ENT pathology and having a presumed difficult airway which will be divided in two groups: anatomically difficult airway group according to The Simplified Airway Risk Index Scale(SARI), with a SARI score  $\geq 5$ , and patients with obstructing airway pathology: oropharyngeal tumors, cervical masses, previous neck surgery or radiotherapy, also with predicted difficult intubation forming group 2.

The two groups are needed because ENT pathology is generating a particular challenge in airway approach which is different from the rest of the pathology and the main goal is to show the efficiency of Rigid Tube for Laryngoscopy (RTL) versus gold standard in intubating patients with various types of airway issues. We decided to include at least ten patients in each group, a reasonable number for testing a new method of airway control. Signed informed consent was obtained from all patients explaining the procedure in simple words and detailing the risks and the safety measures.

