### **Exclusion criteria**

Stridor or marked laryngeal or tracheal stenosis, vocal cords polyps, emergency surgery, high aspiration risk, decompensated cardiac and pulmonary disease, very poor dentition and patient refusal were criteria of exclusion from the study. We've also decided to reject from the study patients who exhibit a Cormack-Lehane grade 1 glottis view when conventional laryngoscopy is performed. In case of difficult mask ventilation causing marked desaturation, requiring prompt action to secure the airway, we will take the first chance to secure the airway considering potentially unsafe the use of the experimental RTL. The

investigator underwent a training period before starting the study, consisting in ten direct laryngoscopies with the RTL under an ENT specialist guidance to get used to manoeuvring the RTL and acquire a reasonable level of skill in using it.

A pre-anaesthetic exam was performed with careful assessment of the airway. Patients with features predictive for difficult intubation gathering at least 4 points on the SARI score and with no known airway pathology were included in group 1. Patients from the group 2, with obstructing airway pathology had a perioperative endoscopic examination of the airway with a flexible rhino-laryngoscope which is meant to evaluate the distorted anatomy and exclude glottic or subglottic stenosis which could contraindicate blind intubation over an intubating tube introducer (gum elastic bougie).

Premedication consisted of 1 or 2 mg of Midazolam given intravenously 15 minutes before the intervention, in the preoperative room. Standard hemodynamic and respiratory monitoring were applied: ECG, non-invasive arterial blood pressure, oxygen saturation, respiratory frequency, end-tidal CO2. Difficult airway kit was prepared. The RTL was in position with the light source attached. Patients were pre oxygenated for 5 minutes and induction of anesthesia with propofol- succinylcholine and fentanyl was performed. After 1 minute of mask ventilation, we noted the oxygen saturation on the pulse oximeter, classical laryngoscopy was performed with a McIntosh curved blade laryngoscope, and CormackLehane glottis visualization was registered- possible values: 1,2,3,3.5,4.

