The RTL intubation starts with the head in extension and in sniffing position, using a retromolar approach, with teeth protection. The approaching side was chosen based on patient pathology and it could be changed during the procedure if the investigator considered so. We used a 1.2-2.2 cm wide and 15-30 cm long tube depending on patient preoperative assessment and pathology. During advancement of the RTL, the investigator is careful to apply the minimum of pressure so the oro-pharyngeal tissue and dentition should not be injured. The RTL was advanced slowly until it reached the epiglottis, then the

epiglottis was lifted, and the vocal cords visualised. The thyroid cartilage was a land point when advancing the RTL, keeping the RTL on its direction and holding pressure on it and thus adjusting the larynx position so the epiglottis and glottis should be easier to visualise with the RTL. After a proper alignment between the RTL and the glottis was achieved, the bougie was introduced through the RTL into the glottis, the RTL extracted, and the standard cuffed intubating tube with lubricated tip was placed in the trachea gently, over the bougie. Secretions were aspirated through the RTL as needed. If the glottis is visualised during the RTL advancement, it will be withdrawing slowly, and the larynx will be manipulated with the left hand from the thyroid cartilage until the glottis comes into sight. A second attempt will be started advancing slower, heading to the thyroid cartilage while looking for epiglottis. Once epiglottis is lifted the RTL must be directed as anteriorly as possible, returning to the epiglottis and starting new lifting if not successful. We decided to stop the attempt at 120 s or if the patient desaturated to 80%.

We note the Cormack-Lehane glottis visualization at classical laryngoscopy- with values ranging from 1 to 4, the time from classical laryngoscopy until the airway was secured in seconds, the lowest oxygen saturation during the procedure and any other complications occurring during procedure. we document every patient data regarding airway, ENT pathology and difficult airway history. We recorded images to document the challenging cases and prove the efficiency of the RTL. We also took notice of any complications that may have arisen during or after the procedure.

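### The plan cannot support its main goal of RTL efficiency against a gold standard: no conventional intubation outcome is described, and RTL intubation success is neither recorded nor analysed

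*Combined protocol and SAP*

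**What the plan says.** The document is a combined protocol and SAP.

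- **Goal (Inclusion criteria).** The text states that "the main goal is to show the efficiency of Rigid Tube for Laryngoscopy (RTL) versus gold standard in intubating patients". The two groups are patients with an anatomically difficult airway and patients with obstructing airway pathology.
- **Size (Inclusion criteria).** "We decided to include at least ten patients in each group, a reasonable number for testing a new method of airway control".
- **Use of the conventional device (procedure text under Exclusion criteria).** After induction, "classical laryngoscopy was performed with a McIntosh curved blade laryngoscope, and CormackLehane glottis visualization was registered". Patients with a grade 1 conventional view leave the study: "We've also decided to reject from the study patients who exhibit a Cormack-Lehane grade 1 glottis view when conventional laryngoscopy is performed". The text then moves to intubation through the RTL over a bougie.
- **End of an attempt (same section).** "We decided to stop the attempt at 120 s or if the patient desaturated to 80" per cent. A second RTL attempt is also described.
- **Data recorded (same section).** The view item reads "We note the Cormack-Lehane glottis visualization at classical laryngoscopy- with values ranging from 1 to 4". A single duration is kept for each patient, worded as "the time from classical laryngoscopy until the airway was secured in seconds". Also listed are the nadir of oxygen saturation, complications, and background airway data. On images, the text says: "We recorded images to document the challenging cases and prove the efficiency of the RTL".
- **Analysis (Statistical analysis plan).** Besides a baseline table, four items are listed: two times, one for conventional laryngoscopy and one for RTL intubation (mean and SD); glottis grade (median and range); lowest saturation (mean and SD); and complications. No success or failure outcome, comparison, test or interval appears.

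**The concern.** The goal is comparative and concerns intubation. To meet it, the study would need the same intubation outcome for the RTL and for a comparator. The plan gives the comparator a view grade and a laryngoscopy time, and neither is an intubation outcome.

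The plan also leaves out the first result a reader would look for: in how many patients given the RTL was the trachea intubated with it? The protocol's own stopping rule means an RTL attempt can end without intubation. With no success count, a stopped attempt could be left out of the mean time, or timed until another technique secured the airway, and a reader could not tell which. Images of challenging cases do not replace a count with a denominator.

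At stake is a report that claims efficiency against a gold standard with no comparator outcome and no stated success rate.

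**Working it through.** **The plan's own figure.** The only design figure is at least ten patients per group, so at least 20 in all. It cannot be reproduced, because the document gives no significance level, power, effect size, standard deviation, success rate or margin.

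**What the goal needs, set against what the plan provides.**

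| Needed | Conventional device | RTL |
|---|---|---|
| Intubation attempt described | No; view graded only | Yes |
| Intubation success recorded | No | No |
| Intubation success analysed | No | No |
| Own time recorded | No; one combined interval | No; one combined interval |
| Time listed for analysis | Laryngoscopy | Intubation |

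**Times.** The procedure text records 1 interval, from classical laryngoscopy to a secured airway. The Statistical analysis plan lists 2. The single interval does not yield both unless a further time point is noted, and none is named. The two listed times also measure different tasks: looking at the larynx with one device and intubating with the other. Neither section says how an attempt stopped at 120 s or at 80% saturation enters the mean.

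**Denominator.** Not every recruited patient need receive the RTL. Grade 1 views are rejected, and the protocol does not use the RTL when difficult mask ventilation causes marked desaturation. The number in whom the RTL was started must therefore be reported; it cannot be assumed.

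**What a success outcome could show at the planned minimum.** Inputs: n = 10 per group (Inclusion criteria), assuming that all ten receive the RTL, which the document does not say. The success counts x are illustrations. Exact (Clopper-Pearson) 95% limits are:

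- lower = 0.025 quantile of Beta(x, n − x + 1)
- upper = 0.975 quantile of Beta(x + 1, n − x), or 100% if x = n

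For x = n the lower limit reduces to 0.025^(1/n).

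| Successes | Exact 95% interval |
|---|---|
| 10 of 10 | 69.2% to 100% |
| 9 of 10 | 55.5% to 99.7% |
| 8 of 10 | 44.4% to 97.5% |
| 20 of 20 (both groups) | 83.2% to 100% |

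With 10 of 10, a failure rate of up to 100 − 69.2 = 30.8% remains compatible with the data in that group.

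**Would failures be expected?** The document gives no success rate, so I assume a range. The chance of at least one failure in ten patients is 1 − p^10:

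- p = 0.9: 1 − 0.9^10 = 65%
- p = 0.8: 1 − 0.8^10 = 89%
- p = 0.7: 1 − 0.7^10 = 97%

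Across this range a failure is more likely than not in each group, so the plan needs a place to count failures.

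**The case against.** The best defence is that this is a small descriptive study with one loose phrase. The Statistical analysis plan plans no test or between-device contrast, and the comparative wording is a single clause in a sentence explaining why two groups are needed. That stands, and it is why the repair is mainly one of wording. It does not remove the mismatch, because that clause is the stated main goal. Success is also a basic result for a descriptive study of an intubation device.

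A second defence is that failures would surface as complications, as a missing time to secured airway, or in the individual airway notes. They might. None of these is defined as failure, however, and no denominator is attached. That stopped attempts would be left out of the mean is a possibility the plan leaves open, not a practice it describes.

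Some stronger readings are tempting but not supported:

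- *The gold standard is unknown.* The term is not defined in the available text, but Macintosh laryngoscopy is readily inferred as the comparator. An opening part of the document was not available, so a definition there cannot be ruled out. The point does not depend on it: the Macintosh has no intubation outcome under either reading.
- *Rejecting grade 1 views biases a view comparison towards the RTL.* That would need an RTL view. The protocol specifies only the classical view and plans no such comparison. Restricting the RTL to patients with a worse conventional view is not in itself a fault.
- *The view and saturation items are ambiguous.* The natural reading is that the view is the classical one and the saturation is the lowest over the single sequence in which both devices are used.

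**Conclusion.** The concern holds. Followed as written, the study can describe aspects of RTL use in selected patients. It cannot show efficiency against a conventional technique, and it need not report how often RTL intubation succeeded. The mismatch between one recorded interval and two analysed times is plain from the text.

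The conclusion is structural and does not depend on the intervals. Those show only what an added success outcome could support: at the minimum of ten per group, if all receive the RTL, complete success would still allow a failure rate of up to about 31% in that group. More than ten per group would narrow this. That precision suits a descriptive claim. Because the defect touches both the main goal and the main result, it should be corrected before any conclusion is drawn.

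**What to change.** 1. **Goal and conclusion.** Restate both as descriptive RTL performance in patients with a conventional view of grade 2 or worse, and drop the comparison with a gold standard. Keeping the comparison would need a named comparator and the same intubation outcomes for both devices, which is a different study.
2. **Success outcome.** Add RTL intubation success per patient, by group. The denominator is all patients in whom the RTL was started, with an exact 95% confidence interval. Define an attempt, and report first-attempt and overall success separately. Count a patient as an overall failure only if the trachea was not intubated with the RTL on any attempt the protocol allows. Recording the RTL view is optional.
3. **Times.** Reconcile the single interval in the procedure text with the two times in the Statistical analysis plan, and define the start and end of each. Report RTL time among successes beside the number of failures, so that the mean is not read as the result for all patients.
4. **Patient flow.** Report how many recruited patients were rejected as grade 1, how many were not given the RTL for other reasons, and how many received it, where records exist.

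The cost is rewording of the goal and analysis plan, case-form entries for success by attempt and for the interval end points, and a flow count. No extra patients or procedures are needed, and no clinical rule changes. The downside is a narrower claim with wide intervals. The document does not say that records of rejected patients or separate device times are kept. If collection has closed, items 2 to 4 may be only partly recoverable, and the report should say what is missing.

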### **Statistical analysis plan**

The statistical part will consist of creating a table with the pre-anaesthetic and demographic variables – mean and standard deviation. The results will be included in a table and graphic image and the data which will be analysed are:

- time for conventional laryngoscopy and for intubation with the RTL- mean and SD
- grade of glottis view as from Cormack-Lehane scale- median and full range

- haemoglobin oxygen saturation during the procedure with the lowest noted as mean and SD
- complications during and after the procedure

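### The aim to show the RTL's efficiency with at least ten patients per group goes beyond what an analysis without any interval can support

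*Combined protocol and SAP*

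**What the plan says.** The Inclusion criteria section states that "the main goal is to show the efficiency of Rigid Tube for Laryngoscopy (RTL) versus gold standard". The sample rests on one sentence: "We decided to include at least ten patients in each group, a reasonable number for testing a new method of airway control". The procedure text, under the Exclusion criteria heading, adds: "We recorded images to document the challenging cases and prove the efficiency of the RTL". It also ends an RTL attempt at 120 s or at a saturation of 80%.

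The Statistical analysis plan is descriptive throughout. It opens with "The statistical part will consist of creating a table with the pre-anaesthetic and demographic variables" and then lists four items. The two procedure times and the lowest saturation each get a mean and an SD. The Cormack-Lehane grade gets a median and a range. The last item reads in full "complications during and after the procedure" and has no summary measure and no denominator. The plan contains no confidence interval, test, precision target or success criterion. RTL success is not among the listed outcomes.

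**The concern.** Showing or proving efficiency against a standard is a claim about patients beyond those studied, and such a claim needs a statement of uncertainty. The planned summaries give none. An SD describes how much patients differ from one another, not how well the mean is known. A median with its range describes the patients observed. A bare complication count, if one is given at all, does not say which rates it rules out.

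The result most likely to be over-read is the favourable one: every RTL intubation succeeds and no complication is noted. Followed to the letter, the plan could present that as having shown efficiency, although the data would remain compatible with a substantial failure or complication rate.

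**Working it through.** **Inputs.** At least 10 patients per group and two groups, so at least 20 in total (Inclusion criteria). The documents state no confidence level, power, expected rate, SD or precision target. The 95% level below is therefore an assumption, and the figures apply if recruitment stops at the minimum.

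**Step 1: the plan's own figure.** Ten per group cannot be reproduced, because a sample size formula has no inputs to work with. The only basis given is that the number is reasonable.

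**Step 2: extreme results.** For 0 events in n, the two-sided exact (Clopper-Pearson) 95% upper limit is 1 − 0.025^(1/n). For n successes in n, the lower limit is 0.025^(1/n).

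| n | 0.025^(1/n) | 0 of n events | n of n successes |
|---|---|---|---|
| 10 | 0.6915 | 0 to 30.8% | 69.2 to 100% |
| 20 (pooled) | 0.8316 | 0 to 16.8% | 83.2 to 100% |

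One failure widens the picture further: 9 of 10 successes gives 55.5 to 99.7%.

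**Step 3: chance of a clean record.** The probability of no event in n patients when the true rate is p is (1 − p)^n.

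| True rate | n = 10 | n = 20 |
|---|---|---|
| 5% | 0.95^10 = 59.9% | 0.95^20 = 35.8% |
| 10% | 0.90^10 = 34.9% | 0.90^20 = 12.2% |
| 20% | 0.80^10 = 10.7% | 0.80^20 = 1.2% |

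The same figures apply to efficiency. If RTL truly succeeds in 90% of patients, ten out of ten occurs with probability 34.9%; if in 80%, with probability 10.7%.

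**Step 4: means.** The half-width of a 95% t interval, in SD units, is t(0.975, n − 1)/√n. At n = 10 it is 2.262/3.162 = 0.72 SD; at n = 20 it is 2.093/4.472 = 0.47 SD.

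**Step 5: does the choice of interval matter?** For 0 of 10, the Wilson upper limit is 27.8% and the one-sided 95% exact limit is 25.9%. The message is the same, but the method and level must be stated with the number.

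**Step 6: scale.** For zero events to bring the two-sided exact upper limit down to 10% takes 36 patients, and to 5% takes 72. These show the scale; they are not proposed sample sizes.

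**The case against.** A descriptive series of about ten patients is an accepted way to study a new airway device, and the plan claims neither power nor precision. It calls the number reasonable and no more. Ten is also a minimum, so a larger group would do better than the figures above. A reader who is given a mean, SD and n can work out the t interval, and a count with its n yields the exact interval. On this view the omission is a matter of reporting style.

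Much of this stands. The design is not at fault for being descriptive, and for the means little information is lost. Three things remain:

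- The plan does not stop at describing. It sets out to show, and elsewhere to prove, efficiency against a comparator.
- No upper target is given, so the plan is fulfilled at ten. Pooling to twenty still leaves an upper limit near 17%, and the Inclusion criteria section says the two groups are needed because their airway problems differ.
- For complications the plan promises neither a count nor a denominator, and success is not listed, so a reader could not reconstruct those intervals.

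A reader might infer that the plan intends to declare the device safe on a zero count. The documents do not support that. They state no safety aim, list complications only as data, and themselves call the device's use potentially unsafe in one situation. The complication figures show only how a zero count should be read.

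Adding t intervals everywhere would also go too far. The documents do not say what time, if any, is entered for an RTL attempt that was stopped. An interval for mean RTL time could therefore describe successes only while appearing to cover all attempts.

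**Conclusion.** The point holds as a mismatch between aim and analysis: the stated goal is stronger than the planned summaries can support at the stated minimum sample. At exactly ten per group, a perfect record leaves a failure or complication rate of up to 30.8% within the two-sided exact 95% interval; pooled over twenty, up to 16.8%. These figures rest on the assumed 95% level, on recruitment stopping at the minimum, and on every patient in the group contributing to the denominator.

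The last condition is not secured. Patients with a grade 1 view are rejected at conventional laryngoscopy, and RTL can be bypassed when mask ventilation is difficult. The documents do not say whether the ten are counted before or after these losses.

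It would be wrong to conclude that the sample fails a power or precision claim, since none is made, or that so small a study has no value. It can serve as a feasibility series if described as one.

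**What to change.** **Aim and sample (Inclusion criteria, and the procedure text under Exclusion criteria).** Replace showing and proving efficiency with estimating it. Describe the sample as a feasibility sample of at least ten per group, and state that at n = 10 the two-sided exact 95% upper limit for zero events is 31%.

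**Proportions (Statistical analysis plan).** List RTL success, within the attempt limit the protocol already states, as an outcome. Report success and complications per group as count over denominator with an exact Clopper-Pearson 95% interval. The denominator is all patients in whom RTL was attempted. Report separately those rejected for a grade 1 view and those in whom RTL was bypassed for difficult mask ventilation.

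**Continuous outcomes.** Give a 95% interval for lowest saturation beside the SD, noting that a t interval is approximate for a small sample of values capped at 100%. Report RTL time in successful attempts, labelled as such, next to the number of failures. Do not present a t interval for time as if it covered all attempts.

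Separate intervals do not by themselves estimate the contrast with the gold standard. If that comparison stays in the aim, it needs its own defined measure.

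**Cost.** Changes of wording and reporting only: no extra patients and no change in conduct. The price is that the stated claim becomes less favourable.
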